4.5 Concomitant Medications and Therapies

4.5.1 Previous Therapies

During Screening, patients will be asked about all medications used during the previous 30 days from anticipated first dose. This information will be recorded in the source documentation and appropriate CRF along with the diagnosis or reason for use. If a branded product is being taken, the generic name should be reported, if known.

Patients will not be enrolled into the study if they have received > 100 mg/m² equivalents of daunorubicin (see [Appendix G](#) for conversion table).

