4.2.3 Exclusion Criteria

Patients meeting any one of these exclusion criteria will be prohibited from participating in this study.

1. Received any previous treatment for AML
2. Diagnosed with APL-M3 or CBF-AML
3. Require concomitant chemotherapy, radiation therapy, or immunotherapy. Hydroxyurea is allowed up to the evening before starting (but not within 12 hours) of starting Induction therapy.
4. Received >200 mg/m² equivalents of daunorubicin (see [Appendix G](#) for conversion table)
5. Have a peripheral blast count of $>30,000/\text{mm}^3$ (may use hydroxyurea as in #3 above)
6. Have active central nervous system (CNS) leukemia
7. Have evidence of uncontrolled disseminated intravascular coagulation
8. Have an active, uncontrolled infection
9. Have other life-threatening illness
10. Have other active malignancies or diagnosed with other malignancies within the last 6 months, except nonmelanoma skin cancer or cervical intraepithelial neoplasia
11. Have mental deficits and/or psychiatric history that may compromise the ability to give written informed consent or to comply with the study protocol.
12. Are pregnant and/or nursing

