4.3.2 Study Drug Administration

Induction – Alvocidib and 7+3

- *Days 1, 2, 3:* Alvocidib at a starting dose of 20 mg/m² as a 30-minute (±10 minutes) IV bolus followed by 30 mg/m² administered as a 4-hour (±15 minutes) IV infusion (this is the starting dose for Cohort 1; see [Table 3](#) for assigned alvocidib doses per treatment cohort)
- *Day 4:* Drug-free day
- *Days 5, 6, 7: (7+3)* Daunorubicin 60 mg/m² via IV bolus of up to 15 minutes' (±5 minutes) duration each day followed immediately by;
- *Days 5, 6, 7, 8, 9, 10, 11:* Cytarabine 100 mg/m²/day via continuous 24-hour IV infusion (±2 hours for infusion duration each day)

Reinduction – Alvocidib and 5+2

Patients **with** evidence of residual leukemia defined as >5% bone marrow blasts plus >10% cellularity, based on the Day 14 (±3 days) bone marrow will be eligible to start a second induction cycle (ie, Reinduction) with alvocidib plus 5+2. The second induction cycle with alvocidib plus 5+2 will be allowed per investigator discretion.

- *Days 1, 2, 3:* Alvocidib at same dosage as during Induction
- *Day 4:* Drug-free day
- *Days 5, 6: (5+2)* Daunorubicin 45 mg/m²/day via IV bolus of up to 15 minutes' (±5 minutes) duration each day followed immediately by;
- *Days 5, 6, 7, 8, 9:* Cytarabine 100 mg/m²/day via continuous IV infusion (±2 hours for infusion duration each day)

Consolidation – HiDAC

Consolidation therapy will consist of high-dose cytarabine (HiDAC) which may be initiated at the time of hematologic recovery or within 90 days of recovery. Consolidation therapy may start before complete hematologic recovery after discussion with the Medical Monitor. It is not anticipated that all patients will undergo Consolidation therapy.

- *Days 1, 3, 5:* HiDAC 3 gm/m² IV every 12 hours (1.5 gm/m² in patients aged 60 to 65 years) (ie, a total of 6 doses over the 3-day regimen); lower starting dose may be permitted at the discretion of the Investigator and after discussion with the Medical Monitor

Patients who plan to receive chemotherapy-based consolidation should get a minimum of two cycles of Consolidation up to a maximum of four cycles. Patients proceeding to stem cell transplant for Consolidation should get one cycle of Consolidation, if possible, to ensure disease stability while transplant plans are being made.

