4.4.4 Dose Modifications

During Induction/Reinduction, there will be no dose reductions for alvocidib or cytarabine. Unless an elevation in total bilirubin level is secondary to suspected Gilbert syndrome, hemolysis (as reflected by an increase in indirect bilirubin level), or hepatic leukemic infiltration, the dose of daunorubicin must be reduced by 25% per day per dose if the patient's total direct bilirubin value is ≥ 1.2 mg/dL and ≤ 3 mg/dL, and must be reduced 50% per day per dose if the patient's total direct bilirubin value is > 3 mg/dL on the day of planned daunorubicin administration. Bilirubin adjustment should be based on direct measurement. Patients with serum creatinine concentrations > 3 mg/dL should receive 50% of the planned dose. Daunorubicin must be omitted from subsequent cycles if the patient's lifetime daunorubicin equivalent exceeds 460 mg/m² (see [Appendix G](#) for conversion table) or their left ventricular ejection fraction (LVEF) drops below 45%.

The HiDAC dose may be modified during Consolidation at the discretion Investigator.

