5.1.2 Within 72 Hours Prior to First Dose of Alvocidib

Perform the following activities and evaluations within 72 hours prior to administration of the first dose of alvocidib:

- Collect blood for evaluation of laboratory parameters ([Appendix D](#)):
 - Hematology
 - Full serum chemistry panel

- Collect urine sample for full urinalysis
- Collect urine or serum sample for β -hCG pregnancy test
- Record all concomitant medications including all prescription drugs, nonprescription drugs, and nutritional supplements
- Lumbar puncture for those patients with clinical symptoms suspicious of central nervous system involvement

Review all Inclusion/Exclusion criteria and determine if patient has met all eligibility criteria for inclusion into the study.

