8.4 Eliciting and Reporting Adverse Events

All adverse events, regardless of severity, which occur during the study, will be documented in the study progress notes, and the “Adverse Event” case report form will be completed. This includes both serious and non-serious events. Adverse events occurring from the time of the first dose will be captured.

All adverse events noted by study staff or volunteered by study patients at any time will be recorded. The Principal Investigator or a qualified designated staff physician will conduct clinical assessments of all patients at each scheduled clinic visit. In addition, patients will be queried about any adverse symptoms they have experienced since the previous study visit. In order to avoid bias in eliciting events, suggestive questioning of the patients shall not occur.

Record a laboratory abnormality as an AE if it is associated with clinical sequelae or requires a therapeutic intervention. For both non-laboratory and laboratory abnormalities capture only the highest grade of an event using Start/Stop dates of the longest duration of the AE not the longest duration of the highest grade. If worst grade is captured on a lab drawn between visits, enter the lab under Unscheduled Evaluations. Additional details are provided in the electronic case report form (eCRF) Completion Guidelines.

Adverse events will be reported and described in terms of intensity, seriousness and causality, based on the Principal Investigator’s judgment using protocol-defined definitions. Necessary counter measures will also be reported on the appropriate case report form used to collect concomitant medications.

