APPENDIX G – ASSESSMENT OF PRIOR AND CUMULATIVE ANTHRACYCLINE/ANTHRACENEDIONE EXPOSURE*

	Cumulative Dose Conversion		Daunorubicin isotoxic Dose Equivalent
Doxorubicin :	mg/m ²	Cumulative dose x 1.00 =	mg/m ²
Daunorubicin :	mg/m ²	Cumulative dose x 1.00 =	mg/m ²
Mitoxantrone :	mg/m ²	Cumulative dose x 4.00 =	mg/m ²
Idarubicin :	mg/m ²	Cumulative dose x 5.00 =	mg/m ²
Epirubicin :	mg/m ²	Cumulative dose x 0.67 =	mg/m ²
Patients who have received more than one anthracycline should have each individual agent cumulative dose converted to daunorubicin dose equivalents using these conversion factors, and then added together.			Total Daunorubicin Dose Equivalent: mg/m ²

* adapted from Long-Term Survivor Guidelines, Version 4.0. October, 2013 ©Children’s Oncology Group

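### The protocol gives two limits for prior anthracycline exposure (200 and 100 mg/m²), and the SAP misstates the Reinduction daunorubicin dose and names mitoxantrone as a study drug

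*Protocol*

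**What the plan says.** **Prior exposure.** Exclusion criterion 4, in the Study Summary and again in Protocol 4.2.3, excludes anyone who has received more than "200 mg/m² equivalents of daunorubicin". Protocol 4.5.1 (Previous Therapies) says: "Patients will not be enrolled into the study if they have received" more than "100 mg/m² equivalents of daunorubicin". Both refer to the Appendix G conversion table, which adds up agents: "Patients who have received more than one anthracycline should have each individual agent cumulative dose converted to daunorubicin dose equivalents". At the eligibility check, Protocol 5.1.2 instructs sites: "Review all Inclusion/Exclusion criteria and determine if patient has met all eligibility criteria for inclusion into the study".

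**Reinduction daunorubicin.** Protocol 4.3.2 gives "Daunorubicin 45 mg/m²/day via IV bolus" on Days 5 and 6. The Study Summary and Section 4.1 give the same dose. The SAP synopsis gives 60 mg/m² on those two days.

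**Study drug.** SAP Section 3 defines study drug as alvocidib, cytarabine and mitoxantrone, and SAP 7.9 describes the patients as receiving ACM. The protocol's abbreviation list reserves ACM for the mitoxantrone regimen and calls this trial's regimen ACD. The SAP's own synopsis, its Section 4.2 and its Section 6 all say daunorubicin.

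**The concern.** The two exposure limits are one eligibility criterion with two values. Only the looser value is in the list that Section 5.1.2 points to; the stricter one sits among the concomitant-medication rules. A site that works from the list would enrol a patient whom Section 4.5.1 forbids. It is then unclear whether that patient belongs in the per-protocol population, because SAP 7.1 removes patients who fail an inclusion or exclusion criterion and does not say whether a bar stated elsewhere counts.

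The SAP errors matter because Section 3 is a formal definition that later sections use. SAP 7.7 summarises exposure to study drugs, and SAP 7.10.2 counts adverse events that lead to delay, reduction or discontinuation of study drug. Protocol 4.4.4 allows no reductions of alvocidib or cytarabine in Induction or Reinduction. It does prescribe them for daunorubicin, for example: "the dose of daunorubicin must be reduced by 25% per day per dose" when direct bilirubin is 1.2 to 3 mg/dL. Taken at its word, the SAP omits from its dose-reduction category the one drug for which reductions are prescribed in those phases.

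The footer in the SAP appendices carries the number TPI-ALV-201, although the plan is for TPI-ALV-101. That suggests text carried over from another plan.

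**Working it through.** The plan states no statistical figure on this point, so there is none to reproduce. The check compares the texts and does some dose arithmetic.

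**1. The eligibility band**

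| Prior exposure (daunorubicin equivalents) | Exclusion 4 | Section 4.5.1 |
|---|---|---|
| up to 100 mg/m² | admitted | admitted |
| above 100, up to 200 mg/m² | admitted | barred |
| above 200 mg/m² | barred | barred |

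In doses of each agent, dividing 100 and 200 by the Appendix G factors, the middle row is:

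- doxorubicin or daunorubicin (factor 1.00): above 100, up to 200 mg/m²
- epirubicin (0.67): 100/0.67 = 149.3 to 200/0.67 = 298.5 mg/m²
- mitoxantrone (4.00): 100/4 = 25 to 200/4 = 50 mg/m²
- idarubicin (5.00): 100/5 = 20 to 200/5 = 40 mg/m²

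**2. The two limits against the lifetime cap**

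Protocol 4.1 and 4.4.4 cap lifetime exposure at 460 mg/m². Total = prior + Induction (3 × 60 = 180) + Reinduction (2 × 45 = 90) = prior + 270.

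- Prior 100: 100 + 270 = 370, under the cap.
- Prior 200: 200 + 270 = 470, over by 10. After Induction alone it is 200 + 180 = 380, under the cap.
- Highest prior exposure that leaves room for both courses at full dose: 460 − 270 = 190 mg/m².

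The stricter limit always leaves room for both courses. The looser one does so except above 190 mg/m².

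**3. Reinduction dose**

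- Protocol: 2 × 45 = 90 mg/m² per course. SAP synopsis: 2 × 60 = 120 mg/m² per course. 120/90 = 1.33, so the SAP overstates the course by 33%.
- If the SAP 7.7 listing of expected doses were programmed from the synopsis, a full protocol dose would appear as 45/60 = 75% of expected. That equals 1 − 0.25, the result of the 25% bilirubin reduction in Protocol 4.4.4, so the listing could not tell full dosing from a reduction.

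**4. What the study-drug definition changes**

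- *TEAE window:* essentially unchanged. Alvocidib is given first, on Day 1. Cytarabine ends after daunorubicin in both courses (Day 11 against Day 7 in Induction, Day 9 against Day 6 in Reinduction), and Consolidation is cytarabine alone.
- *Exposure summaries (7.7) and dose-change categories (7.10.2):* daunorubicin is left out on a literal reading.
- *Number of adverse events missed:* cannot be determined. The triggers for reduction in Protocol 4.4.4 are laboratory values (bilirubin and creatinine), and Protocol 8.4 limits what becomes an adverse event: "Record a laboratory abnormality as an AE if it is associated with clinical sequelae or requires a therapeutic intervention".

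**The case against.** The strongest reply accepts the discrepancies and disputes their weight.

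- **Few or no patients may lie in the band.** Previous AML treatment is excluded. SAP 7.6 lists prior leukemogenic therapy as a baseline category, but the same list includes frontline AML therapy, which cannot apply here, so it is weak evidence about this population. That stands. The better argument that the group need not be empty is in the protocol. Exclusion 10 admits patients whose earlier malignancy is inactive and was diagnosed more than 6 months ago, and an exposure limit with a conversion table would have no purpose if nobody could have prior exposure.
- **The 460 mg/m² cap and the LVEF rule protect anyone admitted under the looser limit.** This also stands, and the conflict is not an unguarded cardiac hazard. It does not settle who is eligible.
- **The Reinduction error has almost no reach.** Expected doses appear only in a by-patient listing, and noncompliance in SAP 7.7 is judged against the protocol's schedules. The SAP's sample table shows 2 of 22 patients with Reinduction, though that is a template. This largely stands.
- **Nobody would apply the mitoxantrone definition literally.** A programmer would probably notice, since mitoxantrone is never given. That lowers the chance of harm but leaves a formal definition that contradicts Section 6 of the same plan.
- **Enrolment has probably closed.** SAP 7.4 describes accrual in the past tense. If so, the useful remedy is the SAP statement and not an amendment.

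**Conclusion.** The point holds: all three conflicts are in the current text. The eligibility conflict covers prior exposure above 100 and up to 200 mg/m² of daunorubicin equivalents, and the documents do not show which value was intended. The SAP overstates the Reinduction daunorubicin course by 33% and defines study drug with an agent this trial does not give.

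The consequences are limited. A site can satisfy both limits by applying the stricter one. The per-protocol population serves sensitivity analyses only. The protocol governs what patients receive, and the SAP takes its DLT criteria from the protocol. The reporting effects depend on two assumptions: that the study-drug definition is applied as written, and that expected doses are programmed from the synopsis. The number of patients in the band and the number of adverse events missed cannot be derived from the documents. The sponsor should correct this because an eligibility threshold and a defined term are wrong as written and the corrections cost little.

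**What to change.** **Protocol.** State one prior-exposure limit in the Study Summary, in Section 4.2.3 (criterion 4) and in Section 4.5.1, with the sponsor confirming the value. This is a protocol amendment and needs IRB/IEC approval under Protocol Section 12. If enrolment has closed, state in the SAP instead which limit was applied and whether patients above 100 and up to 200 mg/m² remain in the per-protocol population.

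**SAP.**
- Synopsis: change Reinduction daunorubicin from 60 to 45 mg/m².
- Section 3: replace mitoxantrone with daunorubicin in the study-drug definition.
- Section 7.9: replace ACM with alvocidib plus 7+3 (ACD).
- In the same pass, correct the TPI-ALV-201 footer and remove the mitoxantrone entry from the abbreviations and the frontline-therapy items from Section 7.6.

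The SAP items are wording corrections to make before database lock. No procedures or patients are added.

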4.5.2 Concomitant Therapies

Concomitant therapies are any new or existing medications or therapy taken by the patient including:

- Drugs, including but not limited to, prescription, over-the-counter, birth control pills/patches/hormonal devices, and homeopathic preparations
- Nondrug therapies, including but not limited to, thermal/laser/radiation procedures, vitamins, herbal medicines/supplements.

During the Screening process (up to two weeks prior to anticipated first dose of study drug), information on all concomitant therapies, medications, and procedures will be recorded in the source documents and appropriate CRF along with the diagnosis or reason for use.

Once the patient receives the first dose of study drug, recording of concomitant therapies will be limited to any new medication or modification of an existing medication taken for treatment of an adverse event (AE). These therapies will be recorded in the source documents and appropriate CRF along with the diagnosis or reason for use. Those therapies used for the treatment of an adverse event are to be linked to an AE and documentation of the AE must also be completed (refer to Section 8).

If a branded product is being taken, the generic name should be reported, if known.

4.5.2.1 Mandated / Permitted Therapies

Concomitant medications necessary for the health and well-being of the patient and that do not interfere with study assessments are permitted during the study at the Investigator's discretion. This includes the use of appropriate medications for the treatment of AEs and/or concurrent illnesses under the direction of the Principal Investigator. All such therapies must be recorded in the source and on the appropriate CRF.

In patients with rapidly proliferating disease, hydroxyurea may be administered up to the evening before starting treatment in either Stage, but not within 12 hours prior to dosing.

Investigators are permitted to administer intrathecal (IT) chemotherapy per institutional protocols after Induction (preferably during marrow aplasia), but before starting Consolidation therapy. Additional doses of IT chemotherapy may be administered after discussion with the Medical Monitor.

Medications and procedures that are mandatory or permitted during the study are listed in Section 4.4.1.

4.5.2.2 Prohibited Therapies

The following medications are excluded from concomitant use:

- Antileukemic therapy (chemotherapy, radiation therapy, immunotherapy) within the last 3 weeks prior to the first study drug administration and during the cycle of study treatment.

4.5.3 Birth Control Requirements for Fertile Patients

Sexually active patients and their partners must use an effective method of contraception associated with a low failure rate prior to study entry, for the duration of study participation, and for at least 6 months after the last dose of study drug. The following are considered effective contraceptives: (1) oral contraceptive pill; (2) condom plus spermicide; (3) diaphragm plus spermicide; (4) abstinence; (5) patient or partner surgically sterile; (6) patient or partner more than 2 years post-menopausal; or (7) injectable or implantable agent/device.

4.6 Protocol Deviations

It is expected that this study will be conducted as described in this protocol, except for an emergency situation in which the protection, safety and well-being of the patient requires immediate intervention, based on the judgment of the Principal Investigator (or a responsible, appropriately trained and credentialed professional[s] designated by the Principal Investigator). In the event of a significant deviation from the protocol due to an emergency, accident or error, the Principal Investigator or Designee must contact the Sponsor at the earliest possible time by telephone. This will allow an early joint decision to be made as to whether or not the patient should continue in the study. This decision will be documented in writing by both the Principal Investigator and the Sponsor.

4.7 Other Precautions

Dose adjustments for nonhematologic and hematologic toxicities and laboratory abnormalities will be made according to Section 4.4.1 and Section 4.4.2, respectively.

5. ON-STUDY CLINICAL AND LABORATORY EVALUATIONS

See [Appendix A](#) - Schedule of Events

5.1 Screening (Within 2 Weeks Prior to First Dose of Alvocidib)

5.1.1 Within 2 Weeks Prior to First Dose

- Obtain written informed consent
- Perform bone marrow biopsy and/or aspiration and collect peripheral blood for diagnosis, cytogenetic profiling, MPFC, molecular testing, and assessment of other potential biomarkers
- Record results of molecular testing from bone marrow or peripheral blood that was collected as standard of care
- Collect and document a complete medical history including pathological confirmed diagnosis of AML by WHO criteria, confirmation of newly diagnosed and previously untreated disease, and all other measures of disease and disease symptoms (eg, extramedullary disease)
- Perform a complete physical examination including height (cm) and weight (kg)
- Assess ECOG PS ([Appendix B](#))
- Record vital signs (temperature, heart rate, systolic and diastolic blood pressures)
- Perform 12-lead electrocardiogram (ECG)
- Perform echocardiogram (ECHO) or multigated acquisition (MUGA) scan
- Perform chest radiograph (may omit, if performed/obtained within 30 days prior to anticipated first dose)
- Record all concomitant medications including all prescription drugs, nonprescription drugs, and nutritional supplements taken within the past 2 weeks

5.1.2 Within 72 Hours Prior to First Dose of Alvocidib

Perform the following activities and evaluations within 72 hours prior to administration of the first dose of alvocidib:

- Collect blood for evaluation of laboratory parameters ([Appendix D](#)):
 - Hematology
 - Full serum chemistry panel

- Collect urine sample for full urinalysis
- Collect urine or serum sample for β -hCG pregnancy test
- Record all concomitant medications including all prescription drugs, nonprescription drugs, and nutritional supplements
- Lumbar puncture for those patients with clinical symptoms suspicious of central nervous system involvement

Review all Inclusion/Exclusion criteria and determine if patient has met all eligibility criteria for inclusion into the study.

5.2 Induction – Alvocidib and 7+3

5.2.1 Assessments Required Prior to First Dose

Within 24 hours prior to first dose, patients will be hospitalized to receive supportive care measures and should remain hospitalized at least through completion of chemotherapy. Patients will be discharged after completion of chemotherapy once deemed clinically stable by the investigator.

